AE	Adverse Event/Adverse Experience
CFR	Code of Federal Regulations
CRF	Case Report Form
DSMB	Data and Safety Monitoring Board
FDA	Food and Drug Administration
GCP	Good Clinical Practice
HIPAA	Health Insurance Portability and Accountability Act
IB	Investigator's Brochure
IND	Investigational New Drug Application
IRB	Institutional Review Board
PHI	Protected Health Information
PI	Principal Investigator
SAE	Serious Adverse Event/Serious Adverse Experience
SOP	Standard Operating Procedure

Study Summary

Title	Metformin for the Prevention of Migraine: A Randomized, Double-Blind, Placebo-Controlled, Crossover Study
Running Title	MPEM
Protocol Number	
Phase	Clinical study phase II
Methodology	Randomized, double-blind, placebo-controlled, crossover design
Overall Study Duration	12 months
Subject Participation Duration	32 weeks
Single or Multi-Site	Single
Objectives	Metformin is a safe, well-tolerated AMPK activator that has demonstrated efficacy in preclinical animal models of migraine and chronic pain. The objective of the MPEM Study is to determine if metformin will reduce the number of migraine days per month in patients with high-frequency migraine.
Number of Subjects	40
Diagnosis and Main Inclusion Criteria	Age 18-65 years Diagnosis of migraine with or without aura according to the ICHD-IIIb (2013) 5-25 migraine days per month
Study Product, Dose, Route, Regimen	Metformin 500mg twice daily orally x 11 weeks, the first week of each 12 week treatment period, patients will receive metformin 250mg twice a day or matching placebo. At week 2, the dose will be increased to metformin 500mg twice a day or matching placebo. In case of intolerable side effects, the dose will be reduced to 250mg twice a day.
Duration of Administration	12 weeks
Reference therapy	Matching placebo

Statistical Methodology	
The primary end point is the number of migraine days per month during treatment with metformin vs placebo. The secondary end point is the percentage of patients with >50% reduction in migraine days per month (response rate). Mean 4-week migraine frequency for patients receiving metformin vs placebo treatment will be assessed by using the Hills-Armitage method. Response rate will be assessed by using the McNemar test.

----------------------------	--

1 Introduction

This is a clinical research protocol for a human research study. This document is a protocol for a human research study. This study will be carried out in accordance with the applicable United States government regulations and Mayo Clinic research policies and procedures.

1.1 Background

Migraine is the third most prevalent disease in the world (Vos, 2012). Preventive treatment is indicated in about 40% of individuals with migraines. Although 4 treatments are FDA-approved for prevention of migraine, none were designed to prevent migraine, efficacy is modest, and all have significant adverse-event profiles. As a result, less than 1/3 of migraine sufferers with who are candidates for prevention receive drug treatment and of those who are treated, more than 85% have discontinued the preventive drug within one year. . Medications designed to prevent migraine by addressing disease pathophysiology likely will have improved efficacy and increased tolerability compared with currently available therapies.

Migraine pain is associated with the activation and sensitization of peripheral meningeal nociceptors. As a result, approximately 75% of patients with migraine will have cephalic allodynia during an attack. mTORC1/MAPK are involved with the sensitization of nociceptors, resulting in chronic pain (Price, 2012). AMPK is a negative modulator of the mTORC1/MAPK pathways (Price, 2012) and therefore may be a novel target for the preventive treatment of migraine.

Metformin is a widely available, safe drug used to treat diabetes mellitus; it also is a powerful activator of AMPK. Preclinical data demonstrates efficacy of metformin in animal models of migraine, suggesting that it blocks hyperalgesia and the transformation to chronic pain.

Metformin has been studied in oncologic research as a novel anticancer drug for many types of cancers including prostate, breast, ovarian, and endometrial cancer. Many studies of metformin in nondiabetic patients with cancer have shown tolerability and lack of hypoglycemia at therapeutic doses up to 1,500 mg daily (Dilokthornsakul, 2013; Laskov, 2014).

Micromedex and prior studies as documented in the protocol, metformin alone does not cause hypoglycemia.

- **Micromedex:**
Hypoglycemia has not been reported at usual doses in monotherapy. Hypoglycemia may occur if caloric intake is insufficient, if strenuous exercise occurs without adequate intake of calories, if other glucose lowering agents are used concurrently, or in combination with ethanol use.

We will instruct patients regarding eating well and not using any other glucose lowering agents or drink ethanol during the study.

1.2 *We will educate patients on the symptoms of hypoglycemia including sweating, weakness, tachycardia, tremor, and feelings of nervousness and/or hunger. If they experience these symptoms, the patient can take 4 oz (120 mL) fruit juice; 6 ounces of non-diet soda; or a tablespoon (15 mL) of honey or table sugar. This process may be repeated in 10 to 15 minutes. If there is no improvement, they will be advised to seek immediate medical help.* **Investigational Agent**

Metformin is a widely available, safe drug used to treat diabetes mellitus; it also is a powerful activator of AMPK. Preclinical data demonstrates efficacy of metformin in animal models of migraine, suggesting that it blocks hyperalgesia and the transformation to chronic pain.

Metformin has been studied in oncologic research as a novel anticancer drug for many types of cancers including prostate, breast, ovarian, and endometrial cancer. Many studies of metformin in nondiabetic patients with cancer have shown tolerability and lack of hypoglycemia at therapeutic doses up to 1,500 mg daily (Dilokthornsakul, 2013; Laskov, 2014).

1.3 Preclinical Data

Preliminary experiments in the laboratories of Drs. [name] and [name] have shown that application of the proinflammatory cytokine interleukin-6 (IL-6) to the dura of rats produces allodynia that lasts for 24 hours and is resolved by 48 hours (Figure 1) (Yan, 2012). However, they remain sensitive to normally nonnoxious stimuli such as small changes in pH (here, the application of a pH 6.8 solution to the dura). As shown in Figure 1, only rats that received IL-6 responded to subsequent pH 6.8 stimulation, even though they were all free from allodynia. This shows that an initial headache-like event in rats can prime the nociceptive system to subsequent,

normally subthreshold events. Mechanisms that mediate priming of the dural-afferent nociceptive system in rats may similarly sensitize the analogous system in humans and contribute to the pain of migraine. This could promote development of headaches in response to events that would be considered nonnoxious in those without headaches. Next, rats were given metformin (200 mg/kg, saline vehicle, administered intraperitoneally) the day before and the day of the IL-6 injection. Metformin administration attenuated the initial allodynia due to IL-6, but more importantly, it prevented development of the primed state (Figure 2). Rats treated with metformin did not have allodynia with pH 6.8 stimulation at the 72-hour time point. These data suggest that metformin treatment may have efficacy against individual headache attacks and that it may treat sensitization of the dural-afferent nociceptive system present between migraine attacks.

1.4 Clinical Data to Date

This will be the first clinical data exploring the use of metformin in high-frequency migraine.

1.5 Dose Rationale and Risk/Benefits

Metformin is a widely available, safe drug used to treat diabetes mellitus; it also is a powerful activator of AMPK. Preclinical data demonstrates efficacy of metformin in animal models of migraine, suggesting that it blocks hyperalgesia and the transformation to chronic pain.

Metformin has been studied in oncologic research as a novel anticancer drug for many types of cancers including prostate, breast, ovarian, and endometrial cancer. Many studies of metformin in nondiabetic patients with cancer have shown tolerability and lack of hypoglycemia at therapeutic doses up to 1,500 mg daily (Dilokthornsakul, 2013; Laskov, 2014).

2 Study Objectives

Study Objective 1: To compare the reduction in the number of migraine days per month during 12 weeks of treatment with metformin vs placebo (primary end point).

Hypothesis: Metformin treatment will significantly reduce the number of migraine days per month compared with placebo.

Study Objective 2: To compare the response rate (percentage of patients with a >50% reduction in migraine days per month) during 12 weeks of treatment with metformin vs placebo (secondary end point).

Hypothesis: The response rate to metformin will be significantly greater than the response rate to placebo.

Study Objective 3: To determine the safety and tolerability of metformin in patients with migraine.

Hypothesis: Metformin treatment will be safe and well tolerated, with limited adverse effects.

3 Study Design

3.1 General Design

We will obtain approval from the Mayo Clinic Institutional Review Board, and all patients will provide written, informed consent before study enrollment.

This will be a single-center, double-blind, randomized, placebo-controlled, crossover study.

After study enrollment, patients will be randomized to the Metformin study drug group or the placebo group. The Principal Investigator or patient can't choose the study group. The patient will have an equal chance of being assigned to the Metformin group. Neither the patient or the Principal Investigator will know which study group they are participating in. In case of an emergency, this information will be available.

Patients will undergo a 2-hour oral glucose tolerance test to confirm the absence of diabetes mellitus. Subjects will then keep a paper headache diary for 4 weeks to establish baseline characteristics, including number of migraine days per month, number of moderate to severe headache days per month, and number of days per month of acute medication use. The 4-week baseline period will be followed by 2 treatment periods of 12 weeks each, separated by a

washout period of 4 weeks (total study duration, 32 weeks). During the washout period, we will washout the study drug x 4 weeks.

For the 12-week treatment periods, subjects will receive either metformin 500mg twice daily or matching placebo twice daily. During the first week of each 12 week treatment period, patients will receive metformin 250mg twice a day or matching placebo. At week 2, the dose will be increased to metformin 500mg twice a day or matching placebo. In case of intolerable side effects, the dose will be reduced to 250mg twice a day.

Subjects will have 7 clinic visits. Routine laboratory studies and a pregnancy test will be performed at enrollment and week 20. Abnormal kidney or liver function will exclude subjects. Pregnancy will exclude subjects. General and neurologic examinations will be performed during 2 of the 7 visits. At each visit, subjects will receive medication for the period until the next visit. A paper headache diary will be used for the trial. For every day that the subject has a headache of any type, she or he will record headache characteristics, associated features, and medications used.

The Screening Visit, visit #1, week 0, will be 60 minutes. During this visit, we will do some tests and procedures to confirm study subjects are eligible to take part in this research study such as: review medical history, physical exam, including height, weight, and “vital signs” (blood pressure, temperature, heart and breathing rates), draw a blood sample, 2 hour glucose tolerance test, urine pregnancy test, provide the study subject instructions for completion of the headache diary and provide headache diary.

Visit #2, week 4, will take about 30 minutes. At this visit we will: review the headache diary and provide the participant with a new supply of study drug.

Visit #3, week 10, will be a phone visit and will take about 15 minutes. At this phone visit we will: Review the headache diary.

Visit #4, week 16, will take about 30 minutes. At this visit we will: Review the headache diary and collect any unused study drug.

Visit #5, week 20, will take about 30 minutes. At this visit we will: review interim medical history, conduct a physical exam including height, weight, and “vital signs” (blood pressure, temperature, heart and breathing rates), collect blood sample, pregnancy test, review the headache diary and provide a new supply of study drug.

Visit #6, week 26, will be a phone visit and will take about 15 minutes to review the headache diary.

Study Closeout Visit

Visit #7, week 32, will take about 30 minutes. At this visit we will: review and collect the headache diary, and collect any unused study drug. The primary end point is the number of migraine days per month during treatment with metformin vs placebo. The secondary end point is the percentage of patients with >50% reduction in migraine days per month (response rate). Adverse events will be recorded. Mean 4-week migraine frequency for patients receiving metformin vs placebo treatment will be assessed by using the Hills-Armitage method. Response rate will be assessed by using the McNemar test.

The statistician will create Web-based case report forms using REDCap. Study coordinators will record data using REDCap forms.

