4.1 Inclusion Criteria

Inclusion criteria are as follows: 1) age 18-65 years, 2) a diagnosis of migraine with or without aura for >1 year according to the International Classification of Headache Disorders-IIIb (2013), and 3) 5-25 migraine days per month on average during the preceding 3 months. Women of reproductive ability must use a reliable form of contraception beginning 3 months before study enrollment, throughout the study, and for at least 1 month after study completion.

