4.2 Exclusion Criteria

Exclusion criteria are as follows: 1) a diagnosis of diabetes mellitus or polycystic ovarian syndrome, 2) overuse of acute migraine treatments, 3) failure to respond to 3 or more previous preventive drug treatments, 4) change in dose of migraine-preventive medication within 2 months of beginning the baseline diary phase, 5) initiation of cranial nerve blocks within 2 months of beginning the baseline diary phase, 6) initiation of Botox within 12 months of beginning the baseline diary phase, 7) significant somatic or psychiatric disease, 8) known alcohol or other substance abuse, and 9) pregnant or breastfeeding.

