5.9.4 Return or Destruction of Study Drug

At the completion of the study, there will be a final reconciliation of drug shipped, drug dispensed, drug returns, and drug remaining. This reconciliation will be logged on the drug reconciliation form, signed and dated. Any discrepancies noted will be documented and investigated, prior to return or destruction of unused study drug. Drug destroyed on site will be documented in the study files.

6 Study Procedures

After study enrollment, patients will undergo a 2-hour oral glucose tolerance test to confirm the absence of diabetes mellitus. Subjects will then keep a headache diary for 4 weeks to establish baseline characteristics, including number of migraine days per month, number of moderate to severe headache days per month, and number of days per month of acute medication use. The 4-week baseline period will be followed by 2 treatment periods of 12 weeks each, separated by a washout period of 4 weeks (total study duration, 32 weeks). For the 12-week treatment periods, subjects will receive either metformin 500mg twice daily or matching placebo twice daily.

During the first week of each 12 week treatment period, you will receive metformin 250mg twice a day or matching placebo. At week 2, the dose will be increased to metformin 500mg twice a day or matching placebo. In case of intolerable side effects, the dose will be reduced to 250mg twice a day.

Subjects will have 7 clinic visits. Routine laboratory studies and a pregnancy test will be performed at enrollment and week 20. Abnormal kidney or liver function will exclude subjects. Pregnancy will exclude subjects. General and neurologic examinations will be performed during 2 of the 7 visits. At each visit, subjects will receive medication for the period until the next visit.

7 Statistical Plan

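### No pregnancy test is scheduled at Visit 2 (week 4), when study drug is first supplied; the last one is four weeks old by then

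*Combined protocol and SAP*

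**What the plan says.** Section 3.1 (General Design) fixes the timing: "Routine laboratory studies and a pregnancy test will be performed at enrollment and week 20". Section 6 (Study Procedures) repeats it. The visit-by-visit list in 3.1 agrees:

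- **Visit 1.** "The Screening Visit, visit #1, week 0, will be 60 minutes". Its procedures include "urine pregnancy test, provide the study subject instructions for completion of the headache diary". No drug supply is listed, and the four-week untreated diary baseline follows.
- **Visit 2, week 4.** "At this visit we will: review the headache diary and provide the participant with a new supply of study drug". No pregnancy test is listed.
- **Visit 5, week 20.** Among other items: "collect blood sample, pregnancy test, review the headache diary and provide a new supply of study drug". Test and supply fall at the same visit.

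Pregnancy is an exclusion in section 4.2 ("9) pregnant or breastfeeding"), and sections 3.1 and 6 both add: "Pregnancy will exclude subjects". Section 4.1 sets a contraception rule: "Women of reproductive ability must use a reliable form of contraception beginning 3 months before study enrollment". The rule continues through the study and for at least one month afterwards.

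**The concern.** The exclusion is checked once before treatment, four weeks ahead of the first dose. A conception during those four weeks, or so shortly before week 0 that the urine test misses it, would not be picked up by any scheduled test before drug is released. The next test comes at week 20, four weeks after period 1 has finished.

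Only women of reproductive ability in the metformin-first sequence would be exposed to metformin in this way. In the placebo-first sequence the week 20 test comes before any metformin. What is at stake is the safety of a participant and a pregnancy. Nothing in the efficacy analysis depends on it.

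**Working it through.** The plan gives no figure of its own on this point, so the check is one of schedule, followed by a rough size.

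**Timeline (section 3.1).** Baseline runs from week 0 to 4, period 1 from week 4 to 16, washout from week 16 to 20, and period 2 from week 20 to 32.

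| Period | Last scheduled test before supply | First supply | Gap |
|---|---|---|---|
| 1 | week 0 | week 4 | 4 weeks |
| 2 | week 20 | week 20 | 0 weeks |

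Two phrases could suggest that drug is given at Visit 1. Visit 2 speaks of a new supply, and 3.1 says medication is given at every visit. Neither changes the result, because the Visit 1 list contains no dispensing and the baseline precedes treatment.

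**Opportunities to detect a pregnancy after week 4.** Visit 3 (week 10) is a phone call. The next visit in person is Visit 4 at week 16, which lists diary review and drug return but no test. Section 5.7 describes bottles of 336 capsules. The full schedule in 5.2 uses 7 days × 2 + 77 days × 4 = 322 units, so one bottle would cover a whole period. That a single bottle is issued at Visit 2 is an inference, not something the plan states.

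**Expected conceptions in the window.** The documents give neither the sex split nor a contraceptive failure rate, so both are assumed:

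expected number = n × annual rate × 4/52

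Here n is the number of women of reproductive ability in the metformin-first sequence, at most half of 40.

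| n | 1% per year | 5% per year | 10% per year |
|---|---|---|---|
| 0 | 0 | 0 | 0 |
| 10 | 0.008 | 0.038 | 0.077 |
| 20 | 0.015 | 0.077 | 0.154 |

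**What a week 4 test would leave open.** For the 12 weeks of period 1 the expected number is n × rate × 12/52. At n = 20 this is 0.046 (1%) to 0.46 (10%).

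**Ceiling of exposure for one undetected case.** 7 days × 0.5 g + 77 days × 1.0 g = 80.5 g of metformin over 12 weeks. The documents give no fetal-risk threshold to set this against, so it describes duration and dose and does not measure harm.

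**The case against.** The strongest reply is that this is a preference and not an error. The plan never promises a test at each dispensing. The statement that pregnancy excludes can be read as acting on the two scheduled results, so there is no internal contradiction. The week 20 test sits within a wider mid-study recheck (history, examination, bloods), and the plan accepts the same four-week-old result for kidney and liver function. Section 8.2 requires the team to ask about adverse events at every contact, so 12 weeks of exposure needs a pregnancy that is neither recognised nor reported at week 10 or week 16. The upper figure of 0.15 also needs every metformin-first participant to be a woman of reproductive ability and a high failure rate. With 10 to 14 such women and 1% to 5% per year, it falls to 0.008 (10 × 0.01 × 4/52) to 0.054 (14 × 0.05 × 4/52). Finally, the fix leaves the larger part of the risk open, since period 1 carries three times the expected conceptions of the baseline.

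Much of this stands. There is no contradiction in the text, 12 weeks is an unlikely ceiling, and the probability is small. But the contraception rule and general questioning do not verify status at first dose, and 8.2 does not name pregnancy. Kidney and liver function are not a close parallel, because a new pregnancy is a yes-or-no event that can arise within four weeks in a woman who tested negative. On the share of risk closed, counting conceptions alone understates the benefit. A baseline conception that goes unnoticed is exposed for all 12 weeks, while one in period 1 is exposed for 6 weeks on average if conceptions are evenly spread. In exposure time the baseline contributes 4 × 12 = 48 and period 1 contributes 12 × 6 = 72, so the added test addresses 48/120, or 40%. This ignores the detection lag of a urine test.

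**Conclusion.** The point holds as a minor safety gap in the schedule. Followed as written, the plan would release period 1 drug on a pregnancy result four weeks old, with no further scheduled test until week 20, whereas period 2 drug is supplied at a visit that includes a test. The expected number of affected pregnancies is 0 to about 0.15 for the whole trial, and probably towards the lower end. That range rests on assumed values for the number of women at risk (0 to 20) and the annual failure rate (1% to 10%). The schedule finding itself rests on no assumption. Sample size, endpoint and analysis are unaffected.

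**What to change.** Keep the Visit 1 test. Add a urine pregnancy test at Visit 2 for women of reproductive ability, in both sequences so that the blind is protected, with the result known before the pharmacy releases drug. In sections 3.1 and 6, split the timing sentence in two: laboratory studies stay at enrollment and week 20, and the pregnancy test is listed for enrollment, week 4 and week 20. Add the test to the Visit 2 procedures in 3.1.

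The cost is one urine test per woman of reproductive ability, at most 40 in the trial, and a few minutes at an existing 30-minute visit. The limits should be stated openly. A very recent conception may still be missed, and conceptions during period 1 would remain untested until week 20.

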3.2 Primary Study Endpoints

The primary end point is the number of migraine days per month during treatment with metformin 500mg BID vs placebo for 12 weeks.

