7.1 Sample Size Determination

This will be a single-center, double-blind, randomized, placebo-controlled, crossover study. Crossover designs have been used successfully in migraine trials (Olesen, 1981). Prior migraine trials have suggested that a sample size of 34 patients has 80% power to detect a mean reduction in migraine days of 1.25 days per month, with $\alpha=0.05[Q^1]$ (σ 2.5, ρ 0.5; Hauge, 2009; Silberstein, 2004; Sorensen, 1986). We will enroll 40 subjects to account for an estimated 15% dropout rate.

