7.2 Statistical Methods

The primary end point is the number of migraine days per month during treatment with metformin vs placebo. The secondary end point is the percentage of patients with >50% reduction in migraine days per month (response rate). Mean 4-week migraine frequency for patients receiving metformin vs placebo treatment will be assessed by using the Hills-Armitage method. Response rate will be assessed by using the McNemar test. The frequency of adverse events during metformin treatment will be compared to that during placebo treatment by using the McNemar test.

Descriptive Statistics

Univariate descriptive statistics and frequency distributions will be calculated, as appropriate for all variables.

Handling of Missing Data

Patients will be included in the primary analysis on the basis of intention to treat. Migraine frequency will be calculated using all available follow-up data and converted to units of frequency per four weeks.

Multiplicity

There is a single primary outcome measure. If the primary analysis is statistically significant, the secondary outcome measure will be assessed in order to facilitate interpretation of clinical importance.

Interim Analysis

There will be no interim analysis for early stopping due to efficacy.

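### The protocol requires no diary entry on headache-free days and does not say how blank days are counted, so missed entries may be scored as migraine-free

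*Combined protocol and SAP*

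**What the plan says.** Section 3.1 (General Design) sets the medium: "A paper headache diary will be used for the trial". It then gives the recording rule: "For every day that the subject has a headache of any type, she or he will record headache characteristics, associated features, and medications used". No section asks for an entry on a headache-free day, a daily yes/no, or a minimum number of completed days.

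According to the visit list in section 3.1, staff at screening will "provide the study subject instructions for completion of the headache diary and provide headache diary". The content of those instructions is not given. The diary is reviewed at weeks 4, 10, 16, 20, 26 and 32. The mid-period contacts at weeks 10 and 26 are by telephone; for week 10 the text is "At this phone visit we will: Review the headache diary". No review is said to include a check for days without an entry.

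Section 3.2 defines the outcome: "The primary end point is the number of migraine days per month during treatment with metformin 500mg BID vs placebo for 12 weeks". On missing data, section 7.2 (Statistical Methods) says "Patients will be included in the primary analysis on the basis of intention to treat" and "Migraine frequency will be calculated using all available follow-up data and converted to units of frequency per four weeks". It does not say whether the divisor is calendar days in the period or days with a diary record, nor how a blank day is classed.

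**The concern.** A four-week rate needs a numerator (migraine days) and a denominator (days on which a migraine would have been seen). Under the written rule the diary supplies the first but not clearly the second: two weeks without headache and two weeks without writing can leave the same record. The analyst must then either divide by calendar days, which makes every blank day migraine-free, or decide after the fact which blanks are missing.

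The primary end point and the responder end point both come from this diary. If recording is poorer on one treatment, that treatment looks better. If recording is equally poor on both, the difference between them shrinks. Information lost at the point of recording cannot be restored in the analysis.

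**Working it through.** **Inputs.** From section 7.1: 34 evaluable patients, target 1.25 days per month, 80% power, α = 0.05 (sidedness not stated), σ = 2.5, ρ = 0.5, 15% dropout. From section 4.1: 5 to 25 migraine days per month at entry. From section 3.1: treatment periods of 12 weeks, or 84 days. The non-recording rates below are assumptions.

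**1. The plan's own figure.** SD of the within-patient difference = 2.5 × √(2 × (1 − 0.5)) = 2.5. A two-sided paired t-test with n = 34 and a shift of 1.25 has power 80.8% (noncentral t); n = 33 gives 79.5%. Enrolment is 34 / 0.85 = 40. The stated figures reproduce and are not in dispute.

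**2. Why the denominator matters.** Take a true rate of 10 migraine days per 28 days, with 14 of 84 days unrecorded and migraine equally likely on those days. The diary shows 10/28 × 70 = 25 migraine days.
- Calendar days: 25 / 84 × 28 = 8.33.
- Observed days: 25 / 70 × 28 = 10.0.

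Section 7.2 is compatible with either. The gap of 1.67 days is in one period's level; it enters the treatment contrast only as far as the two treatments differ in it.

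**3. Non-recording that differs by treatment, blanks counted as migraine-free, no true effect.** False difference = m × Δu, where m is the mean number of migraine days per four weeks and Δu the between-treatment difference in the fraction of migraine days unrecorded. Each cell gives the false difference in days and the chance of a significant result (n = 34, SD of difference held at 2.5, nominal 5%).

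| m | Δu = 2 points | Δu = 5 points | Δu = 10 points |
|---|---|---|---|
| 5 | 0.10; 5.6% | 0.25; 8.7% | 0.50; 20.5% |
| 10 | 0.20; 7.4% | 0.50; 20.5% | 1.00; 62% |
| 15 | 0.30; 10.4% | 0.75; 40% | 1.50; 92% |
| 25 | 0.50; 20.5% | 1.25; 81% | 2.50; about 100% |

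The row m = 25 is the top of the entry range and so an upper limit for a sample mean.

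**4. Equal non-recording on both treatments.** The true difference is multiplied by (1 − u). At u = 10%, 1.25 × 0.9 = 1.125 days. Power at n = 34 is 72% if the SD stays at 2.5 and about 81% if the SD shrinks in the same proportion.

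**5. Responder status.** Assume a complete baseline diary and reduction measured from it. A true 40% reduction leaves 60% of baseline days. It reads as exactly 50% when 0.60 × (1 − u) = 0.50, so u = 16.7%. Any higher fraction unrecorded makes that patient a responder.

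**The case against.** The strongest reply is that nobody reading these documents has seen the diary. Section 3.1 says what is written down on a headache day; it does not say that other days are left blank. A dated form with a daily tick-box fits the text, and the screening instructions may require one. This stands, and it limits confidence. It does not supply the missing definition in section 7.2, and if the form already has the box, the repair is only to say so.

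Second, staff review the diary six times, and a long silence from a patient who entered with at least 5 migraine days per month could be noticed. This stands in part. Within a treatment period the reviews are six weeks apart, one of the two is by telephone, no check for blank days is stated, and a query weeks later relies on recall.

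Third, this is a double-blind crossover with 1:1 allocation to sequence. A patient's stable recording habit affects both periods alike, and diary fatigue over time is a period effect that a balanced, period-adjusted analysis largely removes. This stands. What remains is non-recording linked to treatment, for example if side effects alter how fully patients keep the diary.

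A reader might also infer more than the text supports:
- *That the plan scores missing entries as migraine freedom.* No section states that rule; it is the result of one possible reading, a calendar-day divisor.
- *That section 7.2 depends on an observed-day denominator that does not exist.* The section never names observed days, and for a patient with a dated withdrawal a divisor based on follow-up dates could work.
- *That the gap favours metformin.* The direction depends on which treatment has the poorer recording, and the documents give no evidence on that.

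**Conclusion.** The point holds in a limited form, with medium confidence. As the protocol describes the diary, a missed entry and a migraine-free day cannot be separated, and section 7.2 leaves open how a blank day is counted. Unrecorded days may therefore be scored as migraine-free.

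Bias in the primary contrast needs non-recording to differ by treatment. Its size then ranges from minor (0.25 day and about a 9% false-positive chance, for 5 points at 5 migraine days) to as large as the planned effect (1.25 days and about 81%, for 5 points at 25 days). The 62% for 10 points at 10 days is an illustration within that range, not an estimate for this trial. All these figures assume that blanks are counted as migraine-free and that the SD of the difference stays at 2.5; none rests on a non-recording rate from the documents. Equal non-recording creates no false effect but shrinks a true one, and whether that costs power depends on whether the SD shrinks with it. The sample size of 34, with 40 enrolled, is unaffected.

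**What to change.** - **Section 3.1:** require one entry every day, *headache today: yes/no*, with the headache details only if yes.
- **Section 7.2:** define observed days as days with a yes or no entry; compute the rate as migraine days / observed days × 28; treat days without an entry as missing, not as migraine-free.
- **Diary reviews in section 3.1:** have the coordinator check for days without an entry at each review already scheduled.

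The observed-day rate still assumes that missing days resemble recorded ones. A sensitivity analysis that counts blank days as migraine-free would show how much the result depends on this.

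The cost is one tick-box a day on the paper form, a few seconds of daily burden for the subject, and a few sentences of text. No visits or staff are added. If the current form already has a daily box, only the text needs to change.
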